### **10.2 Duration of Response**

Not applicable

### **10.3 Progression-Free Survival**

Not Applicable

### **10.4 Other Response Parameters**

Not applicable

## **11. Data Reporting / Regulatory Considerations**

### **11.1 Data Collection**

The data collection plan for this study is to utilize RedCap and the device data from the gas sample analyses.

### **11.1.1 REDCap**

REDCap (Research Electronic Data Capture) is a free data management software system that is fully supported by the Weill-Cornell Medical Center CTSC. It is a tool for the creation of customized, secure data management systems that include Web-based data-entry forms, reporting tools, and a full array of security features including user and group based privileges, authentication using institution LDAP system, with a full audit trail of data manipulation and export procedures. REDCap is maintained on CTSC-owned servers that are backed up nightly and support encrypted (SSL-based) connections. Nationally, the software is developed, enhanced and supported through a multi-institutional consortium led by the Vanderbilt University CTSA.

## **11.2 Regulatory Considerations**

### **11.2.1 Institutional Review Board/Ethics Committee Approval**

As required by local regulations, the Investigator will ensure all legal aspects are covered, and approval of the appropriate regulatory bodies obtained, before study initiation.

Before initiation of the study at each study center, the protocol, the ICF, other written material given to the patients, and any other relevant study documentation will be submitted to the appropriate Ethics Committee. Written approval of the study and all relevant study information must be obtained before the study center can be initiated or the IP is released to the Investigator. Any necessary extensions or renewals of IRB approval must be obtained for changes to the study, such as amendments to the protocol, the ICF, or other study documentation. The written approval of the IRB together with the approved ICF must be filed in the study files.

The Investigator will report promptly to the IRB any new information that may adversely affect the safety of the patients or the conduct of the study. The Investigator will submit written summaries of the study status to the IRB as required. On completion of the study, the IRB will be notified that the study has ended.

All agreed protocol amendments will be clearly recorded on a protocol amendment form and will be signed and dated by the original protocol approving signatories. All protocol amendments will be submitted to the relevant institutional IRB for approval before implementation, as required by local regulations. The only exception will be when the amendment is necessary to eliminate an immediate hazard to the trial participants. In this case, the necessary action will be taken first, with the relevant protocol amendment following shortly thereafter.

Once protocol amendments or consent form modifications are implemented at the lead site, Weill Cornell Medicine, updated documents will be provided to participating sites, as applicable. Weill Cornell Medicine must approve all consent form changes prior to local IRB submission.

Relevant study documentation will be submitted to the regulatory authorities of the participating countries, according to local/national requirements, for review and approval

before the beginning of the study. On completion of the study, the regulatory authorities will be notified that the study has ended.

#### **11.2.2 Ethical Conduct of the Study**

The Investigators and all parties involved should conduct this study in adherence to the ethical principles based on the Declaration of Helsinki, GCP, ICH guidelines and the applicable national and local laws and regulatory requirements.

This study will be conducted under a protocol reviewed and approved by the applicable ethics committees and investigations will be undertaken by scientifically and medically qualified persons, where the benefits of the study are in proportion to the risks.

#### **11.2.3 Informed Consent**

The investigator or qualified designee must obtain documented consent according to ICH-GCP and local regulations, as applicable, from each potential subject or each subject's legally authorized representative prior to participating in the research study. Subjects who agree to participate will sign the approved informed consent form and will be provided a copy of the signed document.

The initial ICF, any subsequent revised written ICF and any written information provided to the subject must be approved by IRB prior to use. The ICF will adhere to IRB requirements, applicable laws and regulations.

#### **11.2.4 Compliance with Trial Registration and Results Posting Requirements**

Under the terms of the Food and Drug Administration Modernization Act (FDAMA) and the Food and Drug Administration Amendments Act (FDAAA), the Sponsor-Investigator of the trial is solely responsible for determining whether the trial and its results are subject to the requirements for submission to <http://www.clinicaltrials.gov>. Information posted will allow subjects to identify potentially appropriate trials for their disease conditions and pursue participation by calling a central contact number for further information on appropriate trial locations and trial site contact information.

This study will be registered on clinicaltrials.gov.

#### **11.2.5 Record Retention**

Essential documents are those documents that individually and collectively permit evaluation of the study and quality of the data produced. After completion of the study, all documents and data relating to the study will be kept in an orderly manner by the Investigator in a secure study file. Essential documents should be retained for 2 years after the final marketing approval in an ICH region or for at least 2 years since the discontinuation of clinical development of the IP. In addition, all subjects medical records and other source documentation will be kept for the maximum time permitted by the hospital, institution, or medical practice.

### **12. Statistical Considerations**

## 12.1 Study Design/Endpoints

**Research question:** Can detectable levels of bowel gas methane (CH4) and/or hydrogen (H2) be detected in the abdominal cavity when the bowel is open during laparoscopic right colectomy with intracorporeal anastomosis using Perf-Alert™ detection system?

**Research Hypothesis: H1:** Bowel gas, methane (CH4) and/or hydrogen (H2) can be detected in the abdominal cavity when the bowel is open during laparoscopic right colectomy with intracorporeal anastomosis using the Perf-Alert™ detection system.

### Design

Prospective pilot, single-center, single arm, open label, phase 1 investigator-initiated study to determine device ability to detect bowel gas during laparoscopic right colectomy with intracorporeal anastomosis using Perf-Alert™ gas detection system on 20 subjects into 2 Cohorts.

**Cohort 1:** 10 subjects with measurement of bowel gas at 8 predetermined time points during right laparoscopic colectomy as follow:

- Initiation of surgery/laparoscopy start Insufflation
- 2) Abdominal exploration
- 3) Completion of colon mobilization
- 4) Colon transection
- 5) At Colotomy
- 6) At Enterotomy
- 7) Anastomosis completion
- 8) End of surgery- after re-insufflation before closure

**Cohort 2:** 10 subjects with continuous monitoring of bowel gases through the surgery. The level of H2 and CH4 gases will be noted at the 8 predetermined time points during the continuous monitoring as well.

### Primary end point

Level of Hydrogen (H2) and Methane (CH4) gas measured in ppm or mg/L (parts per million or milligrams per liter (mg/L) at 8 time points during the surgery:

- Initiation of surgery/laparoscopy start Insufflation
- 2) Abdominal exploration
- 3) Completion of colon mobilization
- 4) Colon transection
- 5) At Colotomy
- 6) At Enterotomy
- 7) Anastomosis completion
- 8) End of surgery- after re-insufflation before closure

### Secondary endpoint

The response time of the Perf-Alert™ device measured in seconds from obtaining the sample (from opening the valve) to first detecting a gas presence at the device electronic sensors.

**Covariates:**

- Demographics
- Preoperative Diagnosis
- Existing Medical Conditions
- Statin drugs in the last 3 months
- Antibiotics in the last 3 months
- Intra-abdominal pressure
- Anesthetic gases
- Total CO2 volume
- Intraoperative complications

**12.2 Sample Size/Accrual Rate**

As this is a pilot study, a sample of 20 consecutive subject corresponding to the inclusion and exclusion criteria will accrued for the two study cohorts. Cohort 1- 10 subjects and Cohort 2- 10 subjects.

**12.3 Stratification Factors**

No stratification factors and no interim analysis will be done.

**12.4 Analysis of Endpoints**

**12.4.1 Analysis of Primary Endpoints**

The gas sample gas composition will be analyzed automatically by the Perf-Alert™ gas detection system at the 8 different predetermined time points listed in 12.1. The measurements will be recorded in the data collection forms. The maximum value for the particular sample gases – H2 and CH4, will be recorded and included in the descriptive analysis.

Specifically, the presence of Hydrogen (H2) and Methane (CH4) gas measured in ppm or mg/L (parts per million or milligrams per liter (mg/L) at the 8 time points during the surgery will be descriptively assessed. Descriptive statistics (e.g., mean, standard deviation, median, interquartile range, frequency and percent) will be calculated for these parameters. Ninety-five percent confidence intervals will be calculated for all parameters of interest to assess the precision of the obtained estimates. No formal hypothesis testing will be performed in the pilot study. However, pairwise time point comparisons will be evaluated by the paired t-test or Wilcoxon signed-rank test, as appropriate. Due to the small sample size in this pilot study, all analyses will be considered exploratory and hypothesis-generating with no adjustment for multiple comparisons. All p-values will be two-sided with statistical significance evaluated at the 0.05 alpha level. All analyses will be

conducted using SPSS for Windows v.25 (IBM Corp. Released 2016. IBM SPSS Statistics for Windows, Version 24.0. Armonk, NY: IBM Corp).

#### **12.4.2 Analysis of Secondary Endpoints**

Descriptive analysis with measurements of central tendency and dispersion will also be used for the secondary endpoints presentation.

#### **12.5 Interim Analysis**

*Not Applicable*

#### **12.6 Reporting and Exclusions**

##### **12.6.1 Evaluation of Toxicity**

Not applicable

##### **12.6.2 Evaluation of Response**

Not applicable

### **13. Adverse Event Reporting Requirements**

This study will not report specific adverse events, as subjects are undergoing surgery for regular care. Furthermore, the device that will be used to collect and analyze the bowel gases from the abdominal cavity during surgery is not in direct contact with subjects and does add additional physical risk to the subjects. During laparoscopy, the abdominal cavity is being insufflated with carbon dioxide (CO2) gas, and a standard pressure between 12mm -15 mm/Hg is maintained throughout the surgery in the abdominal cavity for visualization through a CO2 insufflation tubing connected with one of the surgical trocars. If the pressure changes, for example, during instrument exchange through the laparoscopic port, the CO2 insufflator automatically starts the CO2 flow, so the pressure could be maintained between 12mm -15 mm/Hg. When a gas sample for the study is collected from the abdominal cavity, the insufflator will simultaneously replace any volume of gas removed with new CO2 gas. Therefore, there is no additional risk to the patient due to the gas sample collection for research during the surgery. All the intraoperative complications, should there be any, would be part of the regular surgical care risk.

However, all intraoperative complications will be collected as part of the study data collection. Also, to ensure safety, the intra-abdominal pressure level will be collected as a data point at the time of sample collection as part of the safety monitoring measure.

Any hydrogen (H2) and methane (CH4) detected by the device at time points when clinically, these gases are not expected to be found in the abdominal cavity, the operating surgeon will be notified.

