## 2.4 Risk/Benefit Assessment

### 2.4.1 Known Potential Risks

No changes in the care or treatment of the patients will be made as a result of this study, it is only intended to be observational, and therefore, minimal risk is anticipated. The technology being studied will not come into direct contact with the patient. A sterile tubing will be connected to the trocar in the patient during the operation. As sterile tubing is routinely connected to trocars, there is little to no physical risk to the patient. The same type of tubing and setup will be used for measurements as the one used for the insufflation of CO2.

Another potential physical risk is the time under anesthesia. The additional amount of time that the patient will be under anesthesia due to the collection of the gas samples will be under 5 minutes, mitigating any increased risk to the patients due to a long duration under anesthesia.

Another potential physical risk is the need to ex-sufflate and re-insufflate the abdomen prior to the final gas sample collection. Ex-sufflation and re-insufflation occur routinely during laparoscopic surgery due to instrument exchange, and since there will be no instruments in the patient during this ex-sufflation/re-insufflation, the risk to the patient will be no higher than the risk during the regular surgical procedure. The surgeon and study personnel will be responsible for triggering the device to sample the intra-abdominal gas at the predefined time points, they will not have direct contact with any bodily fluids or gases. Therefore, we do not anticipate any significant risks or exposure risks to the patients or study personnel.

Finally, a previous clinical study involving the roux-en-y bariatric procedure was conducted with no adverse patient events [11]. Information on this study is available at Clinicaltrials.gov (<https://clinicaltrials.gov/ct2/show/NCT02679118?term=Sentire&cond=Bowel+Perforation&cntry=US&rank=1>)

Another potential risk related to this research is the loss of privacy. However, all the necessary measures will be taken to protect the subject's privacy. The electronic data will be kept in password-protected computers and the paper data will be stored in a locked cabinet in the locked research office located at K802B.

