#### **2.4.3 Assessment of Potential Risks and Benefits**

Given the potential benefits offered by minimizing one of the most consequential and costly complications of laparoscopy, the potential risks of the study are minimal. Specifically, the device to be investigated will not come into contact with the patient at any time and is simply connected via a standard tube set to a trocar in use during the procedure. The tubing utilized is the same as that used to connect the insufflator to the trocar and standard in all laparoscopic procedures. Secondly, the surgeon will not alter the procedure in any way, with the exception of 60-90 second pauses at each time point during sample collection. The total additional anesthesia time required for each subject will be less than 5 minutes. We believe the benefits of this study overweight the risk.

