#### **4.6 Strategies for Recruitment and Retention**

The potential subjects for this study will be identified from the practice of the Colon and Rectal Surgery, through screening of the daily schedule on EPIC. Subjects scheduled for right laparoscopic colectomy with intracorporeal anastomosis for regular treatment of their medical condition will be invited to participate in the study. The subjects willing to participate in the study will be presented with the research informed consent and introduced to the study. Subject understanding of the study will be assessed, and a full understanding of the study has to be demonstrated by the subject before they sign consent. The subjects will be recruited during the preoperative clinic visit or while in-patient

We are targeting to recruit 20 subjects, male and female, of all ethnic groups. No vulnerable populations will be included in the study. The current colorectal practice includes 8 surgeons, and with no competing study, we believe that we will be able to recruit these subjects for 12 months. The participants will not be compensated for their participation in the study. Also, there are no extra visits that have to be made due to the research study. All the procedures are standard of care, except the gas samples.

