#### **13.1 Adverse Event Definition**

This study does not have specific adverse events. All the interventions are part of regular surgical care. The device is not in direct contact with the subject during the surgery. Obtaining the gas sample will remove about 500 ml of gas for 90 seconds (1.5 minutes), which is

automatically replaced by the CO2 inflow simultaneous with gas sample collection. Therefore, it is not anticipated the abdominal pressure to decrease below 12 mm/Hg.

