**13.3 AE/SAE Follow Up**

**Not Applicable.**

**13.4 Time Period and Frequency for Event Assessment and Follow Up**

**Not Applicable**

**14. Unanticipated Problems Involving Risks to Subjects or Others**

**14.1 Definition of Unanticipated Problems Involving Risks to Subjects or Others (UPIRTSO)**

In this study, unanticipated adverse device effect will be defined as any unanticipated adverse device effect, any serious adverse effect on health or safety, or any life-threatening problem or death caused by, or associated with, a device, if that effect, problem, or death was not previously identified in nature, severity, or degree of incidence in the investigational plan or application (including a supplementary plan or application), or any other unanticipated serious problem associated with a device that relates to the rights, safety, or welfare of subjects (21 CFR 812.3(s)).]

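### Section 13 assigns all intraoperative complications to regular surgical care in advance, and no documented per-event relatedness assessment feeds the section 14 reporting route

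*Combined protocol and SAP*

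**What the plan says.** Section 13 reasons that the insufflator replaces whatever gas the device withdraws and concludes: "Therefore, there is no additional risk to the patient due to the gas sample collection for research during the surgery". The next sentence extends this to every event: "All the intraoperative complications, should there be any, would be part of the regular surgical care risk". Section 13.1 adds: "All the interventions are part of regular surgical care". Earlier in section 13 the device is said, as printed, to be something that "is not in direct contact with subjects and does add additional physical risk to the subjects".

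Other sections describe the study steps differently:

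- Section 2.4.1 names anesthesia time added by sampling as a potential physical risk, and then: "Another potential physical risk is the need to ex-sufflate and re-insufflate the abdomen prior to the final gas sample collection". It rates the re-insufflation risk as no higher than that of the regular operation.
- Section 2.4.3 says "the surgeon will not alter the procedure in any way, with the exception of 60-90 second pauses at each time point during sample collection".
- Section 4.6 says "All the procedures are standard of care, except the gas samples".

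On assessment and reporting, section 13.1.2 is marked Not Applicable, although a five-level attribution scale is still printed there as template text. Section 13.1.4 says AEs will not be reported to the IRB. Sections 13.3 and 13.4 are Not Applicable. Sections 13.1.3, 13.2.3 and 15 commit to reporting unanticipated events to the IRB and the manufacturer. Section 14.1 covers, among other things, "any life-threatening problem or death caused by, or associated with, a device", and section 14.1.2 gives the investigator at most 10 working days to report.

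**The concern.** A statement about expected risk has been worded as a statement about the cause of events that have not yet happened. If it is applied as written, a complication that arises during a sampling pause, a gas withdrawal or the re-insufflation for the final sample already has its label.

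Two things are at stake. The first is interpretation: a later statement that no complication was related to the device would rest partly on the rule and not wholly on someone having looked. The second is reporting: section 14 needs a judgement about association with the device, and the plan provides no recorded judgement from which a report would start.

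**Working it through.** The point depends on no sample size, power or event rate, so the check is mainly a comparison of the text.

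**Step 1. Which steps are done for the study?** Four sections give four answers.

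- 2.4.1: sampling time under anesthesia, and ex-sufflation/re-insufflation before the final sample.
- 2.4.3: sampling pauses only; re-insufflation is not mentioned.
- 4.6: gas samples only.
- 13.1: none; everything is regular care.

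These cannot all be right. Section 13.1 contradicts 4.6 directly, and 2.4.3 omits a step that 2.4.1 treats as a study risk.

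**Step 2. Does the reason in section 13 reach its conclusion?** The reason is that CO2 inflow replaces the gas removed. That bears on loss of pressure during withdrawal. It does not address the re-insufflation cycle or the added anesthesia time, yet the conclusion covers all intraoperative complications.

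**Step 3. Is the study exposure more than nominal?** Inputs: 8 time points (section 3.1), a pause of 60 to 90 seconds at each (section 2.4.3), and a stated total of less than 5 minutes of added anesthesia (sections 2.4.1 and 2.4.3).

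- Lower end: 8 × 60 s = 480 s = 8 min.
- Upper end: 8 × 90 s = 720 s = 12 min.
- Pause length implied by the stated total: 5 min = 300 s; 300 s ÷ 8 = 37.5 s per sample.

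This assumes that every pause adds fully to anesthesia time. The pauses may not apply in the same way to Cohort 2, which is monitored continuously. The calculation shows only that study-driven time exists and that its stated total does not match its parts. The main point does not rest on it.

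**Step 4. Follow one hypothetical event through the plan.** Suppose a complication arises during the re-insufflation before the final sample.

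- Sections 13 and 13.1.3: it is recorded as an intraoperative complication.
- Section 13: its cause is already given as regular surgical care.
- Section 13.1.2: no attribution scale is in force.
- Section 13.1.4: it is not reported to the IRB as an AE.
- Section 13.2.1: if it is serious, the section gives two answers, Not Applicable and then that all SAEs go to the IRB.
- Section 14: it is reportable if serious, unanticipated and associated with the device. The investigator has the duty to report, but no section says for which events association is to be assessed or where the answer is recorded.
- Section 8.1: a complication is grounds for withdrawal, and data already collected are then excluded and destroyed. Section 13 says all intraoperative complications are collected.

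The event can reach the IRB and the manufacturer, but only if the investigator makes, unprompted, a judgement that section 13 has already answered the other way.

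**The case against.** The strongest reply is that the sentence in section 13 closes a risk rationale and is not a classification rule. The text continues by promising to collect all intraoperative complications and to record intra-abdominal pressure at sampling as a safety measure. Nothing forbids the investigator from judging an event device-related. Section 2.4.1 rates re-insufflation as no riskier than the regular operation, which agrees with section 13. Safety is neither an objective nor an endpoint, and complications collected to 30 days can be described without attribution labels.

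Much of this stands, and it rules out stronger readings that a reader might infer:

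- That no event could ever be found study-related, or that section 14 would never be triggered. The documents do not support this. Section 14 has its own trigger, which does not refer to section 13, and sections 13.1.3, 13.2.3 and 15 keep reporting of unanticipated events open. Section 13.2.1 also says all SAEs are reported, though under a Not Applicable label.
- That the trial can say nothing about safety. It can still describe the complications it collects.
- That section 13 admits added risk. The words in question are most plausibly missing a "not", since the surrounding argument runs the other way.

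The reply does not remove the narrower point. A forecast that a step carries little risk does not attribute an event that occurs during that step. The only examples that 13.1.3 and 13.2.3 give of reportable events are the device stopping or malfunctioning, not harm to a patient from a study step.

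**Conclusion.** The concern holds in this form: section 13 pre-judges attribution, conflicts with sections 2.4.1, 2.4.3 and 4.6 on what is done for the study, and leaves the existing section 14 route without a documented per-event assessment to feed it. Harms from study steps could be classed as surgical by default, and a finding of no device-related complications would be partly built in.

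The rule covers all 20 planned subjects. How many events it would affect cannot be stated, because the documents give no expected complication count for this operation. The conclusion assumes that section 13 is applied as written, and that the re-insufflation before the last sample is done for the study, as its listing among the study's risks in 2.4.1 implies. It is a point the sponsor should act on. It does not show that reporting is blocked.

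**What to change.** 1. Delete the blanket attribution sentence in section 13, and correct the wording there about the device adding physical risk.
2. Make sections 2.4.1, 2.4.3, 4.6 and 13.1 agree on which steps are done for the study.
3. For each intraoperative and 30-day complication already collected, have the investigator record its relation to the device or to a study step (gas withdrawal, sampling pause, re-insufflation). The scale printed in 13.1.2 would serve, as would an equivalent; remove Not Applicable from that section.
4. State that serious unanticipated events judged possibly related or higher are assessed under section 14.1.2.
5. Resolve the two statements in 13.2.1 on SAE reporting.
6. Reconcile section 8.1 with section 13, so that complication and relatedness records are kept when a subject is withdrawn for a complication. Otherwise the new field could be destroyed in the cases where it matters most.

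The cost is wording changes and one extra field per complication on the existing form. The downside is that an occasional event will be labelled possibly related. No clinical management changes.
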